### **8.2.8 Subgroup Analyses and Effect of Baseline Factors**

Efficacy will be summarized for the key endpoints for the following subgroups:

- HPV-positive vs. HPV negative head/neck cancer
- Subjects with head/neck cancer enrolled in Cohort B and Cohort B2 with prior cetuximab and platinum exposure.

### **8.2.9 Interim Analyses**

#### **8.2.9.1 Efficacy Interim Analyses**

No efficacy interim analyses are planned in this trial.

However, an interim analysis for Cohort A, B, or C may be performed if the rate of enrollment is much slower than anticipated during the course of the trial. An interim analysis for each cohort would only be performed in this study when  $\geq 10$  subjects in the respective cohort have had scans through Week 16. Results will be reviewed by the study team.

For Cohort A, if an interim analysis is conducted and 2 or fewer subjects out of the first 10 subjects with post-baseline imaging scans (Week 16) have a confirmed or unconfirmed response, then enrollment may be paused until response data for the subsequent imaging scan (Week 24) are reviewed for subjects already enrolled in the trial. Enrollment may be resumed if the binomial probability of the observed response rate is  $\geq 80\%$  under the assumption of a  $\geq 20\%$  true response rate (e.g.,  $\geq 4/16$  confirmed or unconfirmed response).

The operating characteristics of the interim analysis rule are provided in [Table 12](#). The power in Cohort A (assuming true ORR of 45%) decreases to ~77% if the interim analysis is conducted.

**Table 12** Operating Characteristics of Interim Analysis Rule for Triple Negative Breast Cancer – Pause Enrollment if  $\leq 2/10$  Subjects Respond

True ORR	Probability of Pausing Enrollment	Probability of Study Success
10%	0.93	<0.01
15%	0.82	<0.01
20%	0.68	0.02
25%	0.53	0.08
30%	0.38	0.21
35%	0.26	0.39
40%	0.17	0.60
45%	0.10	0.77
50%	0.06	0.88

For Cohorts B (HPV negative) and C, if an interim analysis is conducted and 1 or fewer subjects out of the first 10 subjects with post-baseline imaging scans (Week 16) have a confirmed or unconfirmed response, then enrollment may be paused until response data for the subsequent imaging scan (Week 24) are reviewed for subjects already enrolled in the trial. Enrollment may be resumed if the binomial probability of the observed response rate is  $\geq 80\%$  under the assumption of a  $\geq 10\%$  true response rate (e.g.,  $\geq 2/16$  confirmed or unconfirmed response). The operating characteristics of the interim analysis rule are provided in [Table 13](#). The power in Cohort B (HPV negative) and Cohort C (assuming true ORR of 35%) does not substantially decrease from 80% as a result of conducting the interim analysis.

**Table 13** Operating Characteristics of Interim Analysis Rule for Head/Neck Cancer (HPV negative) and Urothelial Cancer– Pause Enrollment if  $\leq 1/10$  subjects respond

True ORR	Probability of Pausing Enrollment	Probability of Study Success
5%	0.91	<0.01
10%	0.74	0.02
15%	0.54	0.09
20%	0.38	0.25
25%	0.25	0.45
30%	0.15	0.65
35%	0.09	0.80
40%	0.05	0.90
45%	0.02	0.95

### 8.2.9.2 Safety Interim Analyses

Although safety monitoring will occur continuously in the study, an assessment of Grade 4/5 drug-related immunologic AEs will be performed after 10 subjects have been enrolled within each cohort for 1 cycle of therapy. Enrollment will be paused if 4 or more subjects out of the first 10 subjects within a cohort experience a Grade 4/5 drug-related immunologic adverse event. Enrollment may be resumed within a cohort only after a full safety evaluation is performed in consultation between the study investigators and the Sponsor.

The estimate of and the upper bound of the 95% confidence interval for the underlying percentage of subjects with a Grade 4/5 drug-related immunologic adverse event given various hypothetical observed number of subjects are provided in Table 14. These calculations are based on the exact binomial method proposed by Clopper and Pearson [41].

Table 14 Estimate of Incidence of Grade 4/5 events and 95% Upper Confidence Bound Based on Hypothetical Number of Subjects with Event Out of 10 Subjects Evaluated

Hypothetical Number of Subjects With Grade 4/5 Event	Estimate of Incidence	95% Upper Confidence Bound †
0	0%	30.9%
1	10%	44.5%
2	20%	55.6%
3	30%	65.2%
4	40%	73.8%
5	50%	81.3%

† Based on the two-tailed exact confidence interval of a binomial proportion [41].

### 8.2.10 Compliance (Medication Adherence)

A day within the study will be considered an On-Therapy day if the subject receives the study medication infusion. The number of days on therapy is the total number of days from the first day of study medication to the date of the last dose of study medication. Compliance with trial treatment administration will be measured by the number of administered infusions divided by the number of infusions that were supposed to be administered as determined by the number of days on therapy.

Summary statistics for the number of Days on Therapy will be provided by treatment group for the FAS population.

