### **5.8.1 Discontinuation of Study Therapy after CR**

Discontinuation of treatment may be considered for subjects who have attained a confirmed CR that have been treated for at least 24 weeks with MK-3475 and had at least two treatments with MK-3475 beyond the date when the initial CR was declared. Subjects who then experience radiographic disease progression may be eligible for up to one year of additional treatment with MK-3475 at the discretion of the investigator if no cancer treatment was administered since the last dose of MK-3475, the subject meets the safety parameters listed in the Inclusion/Exclusion criteria, and the trial is open. Subjects will resume therapy at the same dose and schedule at the time of initial discontinuation. Additional details are provided in Section 7.1.5.2.1.

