### **7.1.5.2 Treatment Period**

#### **7.1.5.2.1 Second Course Phase (Retreatment Period)**

Subjects who stop MK-3475 with SD or better may be eligible for up to one year of additional MK-3475 therapy if they progress after stopping MK-3745. This retreatment is termed the Second Course Phase of this study and is only available if the study remains open and the subject meets the following conditions:

- Either
  - Stopped initial treatment with MK-3475 after attaining an investigator-determined confirmed CR according to RECIST 1.1
    - Was treated for at least 24 weeks with MK-3475 before discontinuing therapy
    - Received at least two treatments with MK-3475 beyond the date when the initial CR was declared

**OR**

- Subject had SD, PR or CR and stopped MK-3475 treatment after 24 months of study therapy for reasons other than disease progression or intolerability

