**AND**

- Experienced an investigator-determined confirmed radiographic disease progression after stopping their initial treatment with MK-3475
- Did not receive any anti-cancer treatment since the last dose of MK-3475
- Have a performance status of 0 or 1 on the ECOG Performance Scale
- Demonstrate adequate organ function as detailed in Section 5.1.2
- Female subject of childbearing potential should have a negative urine or serum pregnancy test within 72 hours prior to receiving retreatment with study medication.
- Female subjects of childbearing potential should be willing to use 2 methods of birth control or be surgically sterile, or abstain from heterosexual activity for the course of the study through 120 days after the last dose of study medication (Reference Section 5.7.2). Subjects of child bearing potential are those who have not been surgically sterilized or have been free from menses for > 1 year.
- Male subjects should agree to use an adequate method of contraception starting with the first dose of study therapy through 120 days after the last dose of study therapy.
- Does not have a history or current evidence of any condition, therapy, or laboratory abnormality that might interfere with the subject's participation for the full duration of the trial or is not in the best interest of the subject to participate, in the opinion of the treating investigator.

Subjects who restart treatment will be retreated at the same dose frequency as when they last received MK-3475. Treatment will be administered for up to one additional year.

Visit requirements are outlined in Section 6.0 – Trial Flow Chart.

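### Days on therapy spans first to last dose, so for retreated subjects the planned off-treatment interval counts as time on therapy and as missed infusions

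*Combined protocol and SAP*

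**What the plan says.** Section 8.2.10 (Compliance) makes three statements that matter here.

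- It opens with a day-level definition: "A day within the study will be considered an On-Therapy day if the subject receives the study medication infusion".
- It then defines the number of days on therapy differently, as "the total number of days from the first day of study medication to the date of the last dose of study medication".
- Compliance is the number of infusions given, "divided by the number of infusions that were supposed to be administered as determined by the number of days on therapy".

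The section commits to summary statistics for Days on Therapy, by treatment group, in the FAS.

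Section 7.1.5.2.1 says that subjects who stop with stable disease or better "may be eligible for up to one year of additional MK-3475 therapy if they progress after stopping" the drug, and adds: "This retreatment is termed the Second Course Phase of this study". There are two routes in. One is a confirmed CR after at least 24 weeks of treatment, where the subject also "had at least two treatments with MK-3475 beyond the date when the initial CR was declared" (Section 5.8.1). The other is completion of 24 months. Either way the subject must first have "Experienced an investigator-determined confirmed radiographic disease progression after stopping their initial treatment with MK-3475".

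Section 8 does not mention retreatment or the Second Course.

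**The concern.** Every retreated subject has an interval off drug that the protocol itself creates. Second Course infusions are study medication given in this study, so the date of last dose falls in the Second Course and the first-to-last-dose span runs across the interval. Section 8.2.10 has no rule that splits the courses or removes the interval.

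The interval therefore enters twice: as time on therapy, and, through the denominator, as infusions that were due and not given. Compliance is meant to show doses missed or withheld. For these subjects a planned stop could not be told apart from missed dosing.

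**Working it through.** The plan states no compliance figure, so there is none to reproduce. The check applies its ratio to a hypothetical subject who misses no dose, whose compliance should be 100%.

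**Inputs from the documents**
- Dosing interval c: 14 days (Cohorts A-D) or 21 days (Cohort B2), unchanged on retreatment (Sections 6.1 to 6.4).
- First course: at least 24 weeks (CR route) or 24 months (Sections 5.8, 7.1.5.2.1).
- Second Course: up to one year (Section 7.1.5.2.1).
- Trial duration: about 42 months from first consent to last subject's last visit (Section 1.0).

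**Assumptions**
- The gap G, from the last dose of the first course to the first dose of the Second Course, is not given. Values of 84, 183 and 364 days are used.
- Second Courses shorter than one year (12 or 26 weeks) are also assumed.

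**Formulas**
- Let n1 and n2 be the doses given in each course. With none missed, the courses span (n1 - 1)c and (n2 - 1)c days.
- Span from first to last dose = (n1 - 1)c + G + (n2 - 1)c.
- Expected infusions = floor(span / c) + 1 = n1 + n2 + floor(G / c) - 1.
- Compliance = (n1 + n2) / expected.
- Days on therapy, counting both end dates = span + 1. The sum within courses is (n1 - 1)c + 1 + (n2 - 1)c + 1, so the overstatement is G - 1 days.

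**Baseline.** A single 24-month course gives 53/53 (Q2W) and 35/35 (Q3W), both 100%. Any shortfall below therefore comes from the gap alone.

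| Schedule and courses | G (days) | Given | Span (days) | Expected | Compliance |
|---|---|---|---|---|---|
| Q3W, 24 months + 12 months | 84 | 35 + 18 = 53 | 714 + 84 + 357 = 1155 | 56 | 94.6% |
| Q2W, 24 weeks + 12 weeks | 84 | 13 + 7 = 20 | 168 + 84 + 84 = 336 | 25 | 80.0% |
| Q2W, 24 months + 12 months | 183 | 53 + 27 = 80 | 728 + 183 + 364 = 1275 | 92 | 87.0% |
| Q3W, 24 months + 12 months | 183 | 35 + 18 = 53 | 714 + 183 + 357 = 1254 | 60 | 88.3% |
| Q2W, 24 weeks + 26 weeks | 364 | 12 + 13 = 25 | 154 + 364 + 168 = 686 | 50 | 50.0% |

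The first two rows are the extremes for a 12-week gap across both schedules, first courses of 24 weeks or 24 months, and Second Courses of 12 weeks or 12 months.

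In the last row, days on therapy are 686 + 1 = 687 under the stated rule, against 155 + 169 = 324 within courses. That row counts 12 doses in 24 weeks and 13 in 26 weeks. Counting a dose on the final day as well, as the other rows do, gives 27/52 = 51.9%, so the counting convention hardly matters.

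**Fit to the trial's duration.** At 30.44 days per month, the two 183-day rows span 41.9 and 41.2 months. A gap of about 6 months is therefore the most that a full 24 plus 12 months allows within the 42-month estimate. The last row spans 22.5 months and fits easily.

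**After the fix.** Within courses, expected infusions equal infusions given in every row (for the last, 12 + 13 = 25), and compliance is 100%.

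**The two definitions.** A 12-infusion Q2W course lasts 12 days if only infusion days count and 155 days as a calendar span. The compliance ratio uses only the second definition, but the Days on Therapy summary could be programmed from either.

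**The case against.** The best defence is that no infusion was due while treatment was stopped, so a sensible programmer would leave the interval out of the denominator. The same sentence, however, fixes the due number by days on therapy: "infusions that were supposed to be administered as determined by the number of days on therapy". Even if the defence were accepted, it would rescue only compliance. Days on Therapy would still include the gap.

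The limits on the consequences do stand:

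- A reader might infer that retreated subjects will be reported as poorly compliant. The plan sets no threshold for poor compliance and specifies no subject-level report. A 12-week gap after a 24-month course still leaves about 92-95%.
- A reader might infer that the tolerability conclusion is distorted. Section 8.2.5.2 rests tolerability on adverse events, laboratory tests and vital signs, in the ASaT population. Extent of exposure (Section 8.2.11) counts cycles with an infusion, so the gap cannot inflate it.
- A tempting illustration is 24 months, a one-year gap and a further year, which gives about 76%. It runs to about 47 months, against an estimated 42 for the whole trial, and retreatment is available only while the study is open.
- Few subjects are likely to qualify. They must stop in confirmed CR or complete 24 months, then progress, take no other cancer treatment and restart before the study closes. Sections 1.0 and 5.10 also move subjects to an extension trial at study end.
- The conflicting day-level sentence does not enter the compliance ratio.

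**Conclusion.** The point holds as a minor defect in a descriptive measure. Followed as written, Section 8.2.10 overstates Days on Therapy and understates compliance for any subject who enters the Second Course, and nothing else in Section 8 corrects it.

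The direction follows from the text. The size rests on an assumed gap: about 80-95% for 12 weeks, 87-88% for the longest gap that fits a full 24 plus 12 months, and as low as 50% for an early CR stop followed by a year off drug. Longer gaps or shorter courses would give lower values. The number of subjects affected is unknown and probably small, so group summaries may move little.

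No efficacy or safety test depends on these figures. The documents do not support extending the point to exposure, tolerability or a finding of poor adherence.

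**What to change.** In Section 8.2.10, compute days on therapy and expected infusions separately for the initial course and the Second Course, each from first to last dose of that course. Report both measures by course. Define any overall figure as summed days, and as total infusions given over the summed expected infusions. Remove or reconcile the opening sentence on On-Therapy days so that one definition remains.

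This costs one or two SAP sentences and changes no trial procedure. The case report form is not among the documents, but Sections 6.1 to 6.4 schedule treatment administration separately for the two courses, so each dosing date should be assignable to its course.

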## **2.0 TRIAL DESIGN**

### **2.1 Trial Design**

This is a multicenter, nonrandomized, multi-cohort trial of MK-3475 in subjects with advanced solid tumors. Subjects will be enrolled into Cohort A for triple negative breast cancer (TNBC), Cohort B for the initial head and neck (H/N) cancer cohort and Cohort B2 for the H/N cancer expansion cohort, Cohort C for urothelial tract cancer, or Cohort D for gastric cancer. Only subjects with PD-L1 positive tumors will be enrolled in Cohorts A, B, C and D. Subjects in Cohort B2 may be enrolled regardless of PD-L1 status. Approximately 114 subjects were planned to be enrolled in Cohorts A, B, C and D of this trial to examine the safety and efficacy of MK-3475 in these populations. Approximately 110 subjects will be enrolled into Cohort B2 of the study to further explore the safety and efficacy in the head and neck cancer population at a different dose and schedule of MK-3475 and including both PD-L1 positive and negative subjects. Subjects enrolled in Cohorts A, B, C and D will receive 10 mg/kg of MK-3475 administered every 2 weeks. Subjects enrolled in Cohort B2 will receive 200 mg of MK-3475 administered every 3 weeks. Subjects will be evaluated every 8 weeks (56 days  $\pm$  7 days) with radiographic imaging to assess response to treatment. RECIST 1.1 response rate as assessed by independent central radiology review will be used as the primary efficacy endpoint for Cohorts A, B, C and D. RECIST 1.1 response rate as assessed by independent central radiology review will be used as the primary efficacy endpoint for Cohort B2. RECIST 1.1 will be adapted as described in Section 4.2.3.1 to accommodate for the tumor response patterns seen with MK-3475 treatment (e.g., tumor flare), and this adapted RECIST will be used by the sites for treatment decisions in all cohorts. Adverse events will be monitored throughout the trial and graded in severity according to the guidelines outlined in the NCI Common Terminology Criteria for Adverse Events (CTCAE) version 4.0. Treatment with MK-3475 will continue until documented disease progression, unacceptable adverse event(s), intercurrent illness that prevents further administration of treatment, investigator's decision to withdraw the subject, subject withdraws consent, pregnancy of the subject, noncompliance with trial treatment or procedure requirements, completion of 24 months of treatment with MK-3475, or administrative reasons. Subjects who attain an investigator-determined confirmed complete response (CR) may consider stopping trial treatment after receiving at least 24 weeks of treatment. Subjects who discontinue after at least 24 months of therapy for reasons other than disease progression or intolerability or who discontinue after attaining a CR may be eligible for up to one year of retreatment after they have experienced radiographic disease progression. The decision to retreat will be at the discretion of the investigator only if no cancer treatment was administered since the last dose of MK-3475, the subject still meets the safety parameters listed in the Inclusion/Exclusion criteria and the trial remains open (refer to Section 7.1.5.2.1 for further details). After the end of treatment, each subject will be followed for 30 days for adverse event monitoring (serious adverse events will be collected for 90 days after the end of treatment or 30 days after the end of treatment if the subject initiates new anticancer therapy, whichever is earlier). Subjects who discontinue treatment for reasons other than disease progression will have post-treatment follow-up for disease status until disease progression, initiating a non-study cancer treatment, withdrawing consent,

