## **8.2.4 Analysis Populations**

### **8.2.4.1 Efficacy Analysis Populations**

The Full Analysis Set (FAS) population will serve as the primary population for the analysis of efficacy data in this study. The FAS population consists of all randomized subjects in each Cohort who:

- Receive at least one dose of study treatment,
- Have a baseline scan with measurable disease per RECIST 1.1 by independent central radiology review, and
- Have a post baseline scan OR discontinue the trial due to progressive disease/drug related AE

For secondary by Investigator assessment, measurable disease for inclusion in the FAS population will be defined using Investigator assessment of the baseline scan.

A supportive analysis using the All Subjects as Treated (ASaT) population, defined as all randomized subjects, who received at least one dose of study treatment, will be performed for the primary efficacy endpoint(s).

Subjects will be included in the treatment group to which they are randomized for the analysis of efficacy data. Details on the approach to handling missing data are provided in Section 8.2.5 Statistical Methods.

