### **8.2.4.2 Safety Analysis Populations**

The All Subjects as Treated (ASaT) population will be used for the analysis of safety data in this study. The ASaT population consists of all allocated subjects who received at least one dose of study treatment.

At least one laboratory or vital sign measurement obtained subsequent to at least one dose of study treatment is required for inclusion in the analysis of each specific parameter. To assess change from baseline, a baseline measurement is also required.

Details on the approach to handling missing data for safety analyses are provided in Section 8.2.5 Statistical Methods.

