### 8.2.11 Extent of Exposure

Extent of Exposure for a subject is defined as number of cycles in which the subject receives the study medication infusion. Summary statistics will be provided on Extent of Exposure for ASaT population.

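### The compliance ratio counts a dose hold when dosing resumes but drops the same hold when the subject stops, and days on therapy is summarised in the FAS while exposure uses ASaT

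*Combined protocol and SAP*

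**What the plan says.** Section 8.2.10 defines days on therapy as the "total number of days from the first day of study medication to the date of the last dose of study medication". Compliance is infusions administered divided by the "number of infusions that were supposed to be administered as determined by the number of days on therapy". The same section opens with a different notion: "A day within the study will be considered an On-Therapy day if the subject receives the study medication infusion". It gives no rounding rule, does not say whether a dose withheld under the protocol counts as due, and names no analysis population for the ratio.

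On populations, Section 8.2.10 states: "Summary statistics for the number of Days on Therapy will be provided by treatment group for the FAS population". Section 8.2.11, on cycles received, states: "Summary statistics will be provided on Extent of Exposure for ASaT population". Safety is also analysed in ASaT (Sections 8.1.2 and 8.2.4.2): "The ASaT population consists of all allocated subjects who received at least one dose of study treatment". To enter the FAS (Section 8.2.4.1), a treated subject must also have centrally confirmed measurable disease at baseline and must "Have a post baseline scan OR discontinue the trial due to progressive disease/drug related AE".

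Section 5.2.1.2 and Table 3 require pembrolizumab to be withheld for listed toxicities. They allow resumption after recovery, and call for discontinuation if toxicity has not resolved within 12 weeks of the last infusion. The dosing interval is 14 days in Cohorts A to D (Section 2.1: "Subjects enrolled in Cohorts A, B, C and D will receive 10 mg/kg of MK-3475 administered every 2 weeks") and 21 days in Cohort B2.

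**The concern.** Because the window closes at the last infusion, what happens afterwards cannot affect the ratio. Under Table 3, a toxicity hold ends either in resumption or in discontinuation. If dosing resumes, the held doses lie between the first and last infusion and count as due. If it does not, they lie after the last infusion and drop out. The same hold therefore lowers compliance in the subject who recovers and leaves it at 100% in the subject who could not continue.

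That runs the wrong way for a trial whose primary objectives include tolerability of both regimens (Section 3.1, objectives 1 and 3). A reader of the compliance table would take it as evidence on how much of the planned schedule could be delivered, and it would be most flattering where delivery failed for good.

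The population mismatch is a separate matter. Days on therapy and extent of exposure describe the same treatment experience but would be reported on different sets of subjects.

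**Working it through.** The documents give no compliance or days-on-therapy figure to reproduce, so the rule is applied to assumed dosing histories.

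**Inputs from the documents.** Interval c = 14 days (A to D) or 21 days (B2), Section 2.1. Longest gap used: 12 weeks = 84 days, Section 5.2.1.2.

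**Assumptions.** The dosing histories, and the reading that infusions due means scheduled dosing days within the window.

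**Rule in 8.2.10.** With first dose on day F, last dose on day L and A infusions given:

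expected = floor((L − F)/c) + 1; compliance = A/expected.

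**Comparison.** With a stop decision on day D, expected is the number of scheduled days F, F + c, F + 2c, … that fall before D.

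**Hold, then permanent stop.**
- Q2W: doses on Days 1, 15, 29 and 43; stop on Day 43 + 84 = 127. Section 8.2.10: (43 − 1)/14 + 1 = 4 due, 4/4 = 100%. Counting to the stop: Days 1 to 113, (113 − 1)/14 + 1 = 9 due, 4/9 = 44%.
- Q3W: doses on Days 1, 22, 43 and 64; stop on Day 64 + 84 = 148. Section 8.2.10: (64 − 1)/21 + 1 = 4 due, 4/4 = 100%. Counting to the stop: Days 1 to 127, (127 − 1)/21 + 1 = 7 due, 4/7 = 57%.

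**Same hold, then one more dose.**
- Q2W: last dose on Day 127; (127 − 1)/14 + 1 = 10 due, 5/10 = 50%.
- Q3W: last dose on Day 148; (148 − 1)/21 + 1 = 8 due, 5/8 = 63%.

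All histories side by side:

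| History | Q2W, 8.2.10 | Q2W, to stop | Q3W, 8.2.10 | Q3W, to stop |
|---|---|---|---|---|
| 4 doses, stop when the next is due | 4/4 = 100% | 4/4 = 100% | 4/4 = 100% | 4/4 = 100% |
| 4 doses, 3-week gap, stop | 4/4 = 100% | 4/5 = 80% | 4/4 = 100% | 4/4 = 100% |
| 4 doses, 12-week gap, stop | 4/4 = 100% | 4/9 = 44% | 4/4 = 100% | 4/7 = 57% |
| 4 doses, 12-week hold, 1 more dose | 5/10 = 50% | 5/10 = 50% | 5/8 = 63% | 5/8 = 63% |
| Third of 4 doses missed | 3/4 = 75% | 3/4 = 75% | 3/4 = 75% | 3/4 = 75% |
| 1 dose, 12-week gap, stop | 1/1 = 100% | 1/6 = 17% | 1/1 = 100% | 1/4 = 25% |

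**Does the choice about holds matter?** Suppose held doses are never due. On Q2W the 12-week hold covers 5 scheduled doses, so the resumer scores 5/(10 − 5) = 100% and the stopper 4/(9 − 5) = 100%. On Q3W it covers 3, giving 5/(8 − 3) = 100% and 4/(7 − 3) = 100%. If held doses are always due, the pairs are 50% and 44% (Q2W) and 63% and 57% (Q3W). Either convention treats the two subjects alike. Only 8.2.10 gives 50% against 100%, or 63% against 100%.

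**Populations.** Relative to ASaT, the FAS omits treated subjects without centrally confirmed measurable disease, and those with no post-baseline scan who left for a reason other than progression or a drug-related adverse event. The documents do not say how many to expect. Cohort B2 plans about 110 enrolled for 100 evaluable; if evaluable means FAS, which is an assumption, the planning allowance is 10/110 = 9%.

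**The case against.** The strongest objection is that Table 3 requires these holds, so the withheld doses were never supposed to be given and leaving them out is correct. On that view the 44% and 57% measure dose intensity, not adherence. This is a fair reading of adherence, and those two figures are illustrations of another convention, not corrected values. It does not rescue Section 8.2.10, which counts the same protocol-required doses as due whenever dosing resumes.

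The second objection is that little depends on the measure. Primary safety rests on CTCAE-graded events in ASaT. Action taken with treatment is recorded for each event, and reasons for discontinuation (8.2.5.3.1) and cycles received (8.2.11) are reported. That stands, and it keeps the point minor. But cycles received has no expected count beside it, and a discontinuation reason does not show how many doses were held first.

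Third, the FAS is attached to the days-on-therapy summary, not to the ratio, and its last condition retains drug-related discontinuations without a post-baseline scan. Both are true: the FAS does not cause the hold problem, and the population mismatch stands only as a separate inconsistency.

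A reader might also infer more than the text supports:
- That every undelivered dose is invisible. Doses missed between the first and last infusion do count, as the 75% row shows.
- That compliance is 100% by construction because an On-Therapy day is an infusion day. The ratio uses the number of days on therapy, which is defined separately as first to last dose. The On-Therapy sentence is redundant.
- That full adherence exceeds 100%. This needs days divided by cycle length, a formula the SAP does not contain; counting scheduled infusions gives exactly 100%.

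**Conclusion.** The point holds as a minor one. The denominator in Section 8.2.10 ends at the last infusion, so identical holds are counted or dropped according to whether dosing resumes. After four doses and a 12-week hold the contrast is 100% for the subject who stops against 50% (Q2W) or 63% (Q3W) for the one who resumes. The 12-week hold is the long end of the range: with a 3-week trailing gap the two ways of counting differ by 100% against 80% on Q2W and not at all on Q3W, and with no gap beyond one interval they agree.

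These figures rest on assumed individual histories and on counting scheduled doses within the window. The cohort-level effect depends on how many subjects stop after a hold, which the documents do not give. It would be going too far to say that reported adherence is wrong: no adherence figure appears in the documents, and first-to-last dose is a stated convention. What can be said is that the measure is overstated, relative to its own treatment of interior holds, in subjects who stop after one.

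The use of the FAS for days on therapy is a separate inconsistency of unknown size. Neither issue affects a hypothesis test, an efficacy endpoint, a sample size or a stopping rule.

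**What to change.** Amend Section 8.2.10 as follows.

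1. Define expected infusions, for the initial course, as scheduled doses (every 14 days in Cohorts A to D, every 21 days in B2) from the first dose up to but not including the date of the decision to discontinue, or the earliest of 24 months, death or data cut-off if that comes first.
2. Keep the exclusion of the decision date. With Q2W doses on Days 1, 15, 29 and 43 and a decision to stop at the Day 57 visit, including that day gives 1 + 56/14 = 5 due and 4/5 = 80% although no dose was missed. Excluding it gives 4/4 = 100%. State also how the ±3-day dosing window in Section 5.2.2 applies, since a stop decision at a visit one to three days late would otherwise count a missed dose.
3. Report administered over expected by cohort in ASaT. Show protocol-directed holds separately from other missed doses, each treated the same whether or not dosing resumes.
4. Handle the Second Course separately.
5. Summarise days on therapy in ASaT, to match Section 8.2.11.
6. Delete the redundant On-Therapy day sentence.

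The cost is one SAP paragraph and one reprogrammed table, from dosing and discontinuation dates that the trial should already hold. The reported compliance figure will look less favourable. No clinical rule changes.
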